9.3.3 Secondary Outcome Variables; Drug exposure

Everolimus (RAD001) dosing will commence as per current practice. Patients will be instructed to take everolimus (RAD001) orally with a large glass of water, once daily, at the same time each day with or without food. Patients will be instructed to take one tablet of 25mg exemestane orally as per the SmPC.

Confirmation of correct dosing with everolimus and exemestane will be recorded in the eCRF, with details of any interruptions in drug treatment or dosage alterations. Compliance will be assessed by the Investigator and/or study personnel at each visit using tablet counts and information provided by the patient or caregiver. This information should be included in the source document at each visit for both drugs (everolimus and exemestane).

The mean and median duration of exposure will be assessed. A record will also be maintained of any dose modifications with everolimus, including duration and reason(s).

Patients will continue to be treated at the discretion of the treating physician. Information on drug exposure will be collected on the Dosage Administration Record page of the eCRF.

After a patient's individual study involvement ends, routine clinical practice will continue under the direction of the Investigator.

9.3.4 Other Secondary Outcome Variables

Observation intervals are in line with clinical routine: after approximately two weeks, one month and thereafter at monthly to three monthly intervals after the start of treatment with Afinitor and exemestane. Patients will be assessed, as described below, and details will be recorded in the eCRF.

9.3.4.1 Clinical/demographic patient characteristics:

• Physical examination

Significant findings present prior to the start of the study should be documented on the Medical History/Current Medical Conditions eCRF. Significant findings after the start of the study, which meet the definition of an AE, must be recorded on the AE eCRF.

Weight should be measured at screening.

• Vital signs

Vital signs can be recorded on the appropriate eCRF pages.

Vital signs can be measured at screening and throughout the study in accordance with routine clinical practice. Any particular clinical findings seen before starting the study should be documented in the Relevant Medical History eCRF. The findings that are compatible with AEs after commencing the study must be documented on the AE eCRF.

• Laboratory evaluations

Laboratory evaluations are for the clinical management of the patients and these will not be routinely documented in the eCRF.

Any particular clinically significant findings before commencing the study must be documented in the Relevant Medical History/Current Medical Conditions eCRF. Abnormal laboratory parameters that are clinically relevant (e.g., require dose modification and/or interruption of the study drug, lead to clinical symptoms or signs or require therapeutic intervention) constitute an AE and must be recorded on the AE eCRF.

• Haematology:

Haematology tests may include a complete blood count, a total white blood cell count, red blood cell count, haemoglobin, haematocrit and a platelet count.

Tests may be performed at screening and then as clinically indicated during the study. In the event of grades 2, 3 or 4 haematological toxicities that require study drug dose modifications or interruptions, haematological tests should be repeated weekly until recovery to the baseline value or grade 1.

• Clinical chemistry:

Serum chemistry tests include urea, creatinine, lactate dehydrogenase, total protein, electrolytes (sodium, potassium and calcium), total bilirubin, gamma glutamyl transferase, albumin, alkaline phosphatase, aspartate aminotransferase, alanine aminotransferase, uric acid and fasting glucose (ideally fasting state for at least 12 hours).

Serum chemistry should be performed at screening and then as clinically indicated during the study. In the event of grades 2, 3 or 4 non-haematological toxicities that require study drug dose modifications or interruptions, biochemistry tests should be repeated weekly until recovery to the baseline value or grade 1.

• Serum lipid profile:

A serum lipid profile assessment should be performed at screening and then as required during the study. In the event of grades 2, 3 or 4 toxicities, serum lipid tests should be repeated weekly until recovery to the baseline value or grade 1.

• Tumour assessment

Tumour assessment and response will be investigator assessed. Investigator assessed disease progression may be based on clinical examination or radiographic or laboratory features, mirroring routine practice.

The decision regarding patient management will remain with the local Investigator.

• Pulmonary function tests

Pneumonitis is a known AE associated with the use of rapamycin and rapamycin analogues. Pulmonary function tests can be performed at screening (prior to the start of the study) or during the study if clinically indicated and if warranted to exclude or manage NIP. Significant findings must be recorded on the relevant eCRF pages.

9.3.4.2 **Prior and subsequent treatments**

Details of all prior and subsequent treatments for ABC will be collected including the reason(s) for discontinuation.

9.3.4.3 Regimen/concomitant medication

Concomitant medications and changes in additional therapies during the study will be recorded. The impact of any concomitant medications on patient outcomes will be assessed.

9.3.4.4 Performance status

Performance status should be assessed at screening and scored using the ECOG Performance Status Scale.

The ECOG Performance Status Scale Index [Oken MM, 2008] allows patients to be classified for functional impairment. Table 9-3 defines Performance Status scores.

Score	Performance Status
0	Fully active, able to carry on all pre-disease performance without restriction.
1	Restricted in physically strenuous activity but ambulatory and able to carry out work of a light or sedentary nature, e.g., light housework, office work.
2	Ambulatory and capable of all self-care but unable to carry out any work activities. Up and about more than 50% of waking hours.
3	Capable of only limited self-care, confined to bed or chair more than 50% of waking hours.
4	Completely disabled. Cannot carry on any self-care. Totally confined to bed or chair.
5	Dead.

 Table 9-3
 ECOG Performance Status Scale

9.3.4.5 Quality of Life

.

The EuroQoL five dimensional questionnaire (EQ-5D) is a standardised instrument to assess health state values that has been developed, validated and published by the EuroQol Group in 1990. A copy of the questionnaire is included in Annex 3 of this protocol. The EQ-5D consists of two pages; the EQ-5D descriptive system and the EQ visual analogue scale. The EQ-5D descriptive system comprises five dimensions: mobility, self-care, usual activities, pain/discomfort and anxiety/depression. Each dimension has five levels: no problems, slight problems, moderate problems, severe problems and extreme problems.

Subjective well-being (SWB) data are being used to inform public policy in the UK and researchers are considering how these data relate to HRQoL. It has been demonstrated that health is not the only factor affecting QoL, although this has not been considered in the Breast Cancer setting. By collecting both HRQoL and SWB data, this study will add to the evidence on the relationship between the two. It will also highlight the extent to which HRQoL measures capture the full effect of disease and treatment on women with metastatic breast

cancer [HM Treasury 2010, Organisation for Economic Co-Operation and Development 2011, Dolan P 2011].

Both questionnaires are for assessment purposes only and will not form part of the patient's management. The overall score contributes to the secondary endpoints of the study. The overall and subsection scores will be documented in the clinical study report for the secondary endpoint. A change in the score in either questionnaire will not, in itself, be reported as an AE. The scores form part of the evaluation of the disease under study and are, therefore, already incorporated as study endpoints. However, should the Investigator feel that any particular individual parameter is not representative of the underlying disease or represents a clinically significant event, then this will remain reportable as an AE in line with reporting requirements and this review will be documented in the eCRF.

9.3.4.6 Adverse events

Safety will be monitored by assessing all AEs, including Serious Adverse Events (SAEs), the regular monitoring of haematology, blood chemistry, vital signs and physical condition. These assessments should be performed continuously throughout the study.

An AE is any undesirable sign, symptom or medical condition occurring after starting study drug (or therapy) including death. Medical conditions or diseases present before starting the study are only considered AEs if they worsen after starting the study.

A SAE is an undesirable sign, symptom or medical condition which: 1. is fatal or lifethreatening; 2. requires or prolongs hospitalisation; 3. results in persistent or significant disability/incapacity; 4. constitutes a congenital anomaly or a birth defect; 5. is medically significant, in that it may jeopardise the patient and may require medical or surgical intervention to prevent one of the outcomes listed above.

Toxicity will be assessed using the NCI-CTCAE, version 4.03 (CTCAEv4.03, http://evs.nci.nih.gov/ftp1/CTCAE/CTCAE_4.03_2010-06-14_QuickReference_8.5x11.pdf).

9.3.4.7 Study discontinuation

At a minimum, all patients who discontinue the study, whether withdrawn prematurely or otherwise and including those who refuse to return for a final visit, will be contacted for safety evaluations 30 days following end of treatment.

If a study withdrawal occurs, or if the patient fails to return for visits, the Investigator must determine the primary reason for a patient's premature withdrawal from the study and record this information on the End of Treatment eCRF page.

At this stage, the following information will be recorded:

- Date and reason for the end of the study (end of the study, treatment withdrawal, discontinuation of follow-up/lost to follow-up, or any other reason);
- Clinical details including best response during treatment;
- Safety data.

9.3.4.8 Criteria for premature withdrawal

The planned observation period per patient starts with initiation of treatment with Afinitor in combination with exemestane, but ends on completion of the observation phase. The observation phase completes once the last patient has been on study for 12 months. All

antineoplastic therapies (surgery, medication, radiotherapy) for advanced breast cancer both prior to initiation of Afinitor plus exemestane and post discontinuation should be recorded on the relevant eCRF pages.

Patients should be followed until the end of the study except if the following conditions for early termination are met:

- Voluntary discontinuation (withdrawal of patients' consent to collect or use their data);
- Patient lost to follow-up.

All data generated up to withdrawal of consent and the reason(s) for discontinuation will be recorded. Patients who withdraw consent will not be contacted for follow-up information.

Patients who discontinue the study for any reason other than consent withdrawal should be asked to return for an early discontinuation assessment. The reason for discontinuation should be established. All available safety data will be collected for a period of one month following the last dose treatment.

For patients who are lost to follow-up (those whose status is unclear because they fail to appear for study visits without stating an intention to withdraw), the physician should contact the patient and ask them to return for a final assessment. Every effort should be made to obtain a reason for discontinuation. The physician should document steps taken to contact the patient, e.g., dates of telephone calls and registered letters.

9.4 Data sources

Data sources will include patient medical records, including determination of the exposure to the study product and concomitant medication, as well as any adjustment in dosages. Additional sources will include laboratory reports and X-rays. The baseline characteristics, ECOG Performance Status and EQ-5D and SWB questionnaires may be entered directly into the electronic database during the study which will capture, check, store and analyse the data.

Novartis or an appropriate third party will initiate participating sites. Before study initiation, a Novartis representative (or their designee) will review the protocol and eCRF with the physicians and their staff.

Concomitant or prior medications entered into the database will be coded using the World Health Organisation (WHO) Drug Reference List. Medical History/Current Medical Conditions and AEs will be coded using the Medical Dictionary for Regulatory Activities (MedDRA) terminology.

Safety data will be available to Novartis throughout the study on the electronic database.

Data collection schedule

This is a NIS and does not impose a therapy protocol, diagnostic/therapeutic procedure, or a visit schedule. Patients will be treated according to the local prescribing information, and routine medical practice in terms of visit frequency and types of assessments performed and only these data will be collected as part of the study. The observation intervals will be in line with clinical routine e.g. after approximately two weeks, one and three months and thereafter at a three-month interval after the start of treatment with Afinitor and exemestane. The

treating physician will be asked to complete the appropriate eCRF at every patient visit, if possible.

For patients who discontinue prematurely, the reason for discontinuation should be determined.

9.5 Study size

The sample size calculation of 200 patients is based on disease incidence, sample size compared with the overall population, and the expected recruitment within the enrolment period.

The sample size is based on the precision of the estimate of the incidence of the two specific toxicities defined in the primary objective (stomatitis and NIP). Stomatitis is a common AE in patients treated with Afinitor with all grade incidences reported as 71% [Thanopoulou 2014], 59% [Yardley 2013] and 56% [Baselga 2012]. All grade incidences of NIP have been reported as 36% [Thanopoulou 2014], 16% [Yardley 2013], 12% [Baselga 2012] and 39% [Omarini et al 2014].

For a sample size of 200 completed patients, Table 9-4 shows the width of 95% CIs for a range of observed incidences in subjects treated with Afinitor in combination with exemestane for 12 months. For example, when the sample size is 200, an exact (Clopper Pearson) two-sided 95.0% CI for a single proportion will extend 6.8% below to 7.2% above the observed incidence for an expected incidence of 40%.

Table 9-4	Sample Size
N=200 Incidence N (%)	Exact (Clopper Pearson) 95% Cl
20 (10%)	6.2%, 15.0%.
40 (20%)	14.7%, 26.2%
60 (30%)	23.7%, 36.9%.
80 (40%)	33.2%, 47.2%
100 (50%)	42.9%, 57.1%
120 (60%)	52.9%, 66.9%
140 (70%)	63.1%, 76.3%
160 (80%)	73.8%, 85.3%

Sample size calculations were done using StatXact9[®].

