Afinitor is a rapamycin derivative that inhibits mTOR through allosteric binding to mTORC1 but not mTORC2 [Efeyan and Sabatini 2010]. Afinitor combined with AIs in preclinical models of ER+, hormone sensitive and hormone resistant breast cancer, results in G1 arrest and enhanced apoptosis [Boulay 2004]. In the clinic, Afinitor monotherapy demonstrated clinical activity in patients with ABC who had mostly ER+ tumours and had received previous endocrine therapy [Ellard 2009]. In this trial, 19 of the 49 patients enrolled were ER+/HER2-; one complete response (CR), two partial responses (PRs), three stable disease for longer than six months, and six stable disease for less than six months were reported in this subgroup. Median PFS in this subset of 19 patients was 3.5 months (95% CI: 1.9–5.5 months, data source: National Cancer Institute [NCI]-Canada). An additional PR was reported in a patient with ER+ HER2-unknown tumour [Ellard 2009].

the combination of Afinitor with More recently, exemestane showed significant improvement in efficacy, in terms of PFS, response rate, and clinical benefit rate (CBR), relative to exemestane monotherapy [Baselga 2011]. The median locally assessed PFS was 7.8 months for Afinitor plus exemestane versus 3.2 months for exemestane plus placebo (HR: 0.45; 95% CI: 0.38-0.54; P<0.0001). The overall response rate (12.6% versus 1.7%;P<0.0001) and CBR (51.3% versus 26.4%; P<0.0001) were superior in the Afinitor plus exemestane arm compared with the exemestane plus placebo arm. Analyses by central assessment showed a median progression free survival (PFS) of 10.6 months with Afinitor versus 4.1 months with placebo (HR: 0.38; 95% CI: 0.31-0.48; P <0.0001) confirming the results of the primary PFS analysis [Piccart et al 2012, Baselga 2012]. The combination of Afinitor and exemestane has received a marketing authorisation in the USA, EU and many other countries based on the results of this study.

Confidential

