Overall, 20% of patients in the Afinitor plus exemestane arm of the BOLERO-2 study had NIP or related events, compared with <1% in the exemestane alone arm. Grade 3 events occurred in 4% of patients and one grade 4 event was reported. The time course for pneumonitis differed from stomatitis, with few early events and no appreciable plateau. Approximately one-quarter of events (grade \geq 2) occurred within the first 12 weeks (cumulative risk, 5%). Cumulative risks of pneumonitis (grade \geq 2) in the Afinitor plus exemestane arm were 10% and 16% at 24 and 48 weeks, respectively (Figure 2). Among patients with grade 3 pneumonitis in the experimental arm, 80% experienced resolution to grade \leq 1, typically following dose interruption/reduction, after a median of 3.8 weeks. Complete resolution of grade \geq 3 pneumonitis was reported in 75% of patients, after a median of 5.4 weeks.

Figure 2: Cumulative risk estimates for initial onset of grade \geq 2 non-infectious pneumonitis [Rugo 2014]

Abbreviations: EVE, everolimus; EXE, exemestane; PBO, placebo.

8 Research question and objectives

This NIS will prospectively collect UK specific data on the use of Afinitor in combination with exemestane. United Kingdom audit data [Omarini 2014, Thanopoulou 2014] and anecdotal evidence to date has suggested a higher AE incidence than expected from the reported safety profile in the BOLERO-2 study. Of particular interest are two AEs, stomatitis and NIP, both of which are class effects of rapamycin derivatives. Understanding the time course of these AEs will allow appropriate patient education, inform frequency of monitoring and aid in development of prevention and management strategies. The study will also attempt to identify any predisposing risk factors for the development of these two AEs.

8.1 **Primary objective:**

The primary objective of this observational study is to describe, in patients commencing treatment with Afinitor in combination with exemestane for ABC after progression on a NSAI two specific toxicities, namely stomatitis* and NIP* in terms of:

- incidence, severity, length of time to onset, duration and clinical course,
- specific management (prophylaxis and intervention).

The study will also collect data on any possible potential predisposing factors and will include collection of data on past incidence.

*Definition of CTCAE (Common Terminology Criteria for Adverse Events): Non-infectious pneumonitis (NIP) and stomatitis (V4.0 2009)

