9.2 Setting

Approximately 200 postmenopausal women will be recruited in 25 UK centres. Patients will be greater than 18 years of age with ER+ locally advanced or metastatic breast cancer for whom a decision has been taken to initiate treatment with Afinitor (everolimus [RAD001]) in combination with exemestane.. There are no restrictions regarding the last anticancer treatment prior to enrolment. Participating patients may not take part in any clinical study in parallel to this, as this does not constitute routine medical practice and would thus be counter to the objectives of a NIS. Treatment may not be administered for the purpose of inclusion in the NIS, but must be given exclusively for the purpose of medical and therapeutic need.

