9.7.1 Analysis of the primary objective

The primary objective of this study is to evaluate (in patients commencing treatment with Afinitor in combination with exemestane for ABC after progression on a NSAI) two specific toxicities (stomatitis and NIP) in terms of: incidence, severity, length of time to onset, duration and clinical course, specific management (prophylaxis and intervention); and any preventive measures. Incidence, severity, length of time to onset, duration, and clinical course of any instances of stomatitis and/or NIP will be analysed. Specific management of these events, including variables for prophylaxis and interventions, and any preventive measures will also be investigated. Predisposing factors will also be investigated.

The analyses will be solely descriptive and comprise the description of the various items and the 95% CI.

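### Section 9.5 states the precision of Table 9-4 for 200 completed patients treated for 12 months, a cohort that the recruitment target, the analysis population and the quoted PFS medians cannot produce.

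*Protocol*

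**What the plan says.** Protocol section 9.5 justifies 200 patients partly by disease incidence and expected recruitment, and partly by the precision of the estimated incidences of stomatitis and NIP. The precision part is Table 9-4, introduced with "For a sample size of 200 completed patients, Table 9-4 shows the width of 95% CIs for a range of observed incidences in subjects"; the sentence then specifies that these are subjects "treated with Afinitor in combination with exemestane for 12 months". The worked example, for 40% incidence, says that "an exact (Clopper Pearson) two-sided 95.0% CI for a single proportion will extend 6.8% below to 7.2% above the observed incidence".

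Three other parts of the protocol bear on that label:

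- **Recruitment.** Section 9.2: "Approximately 200 postmenopausal women will be recruited in 25 UK centres". The abstract gives the same number. No allowance for loss appears anywhere.
- **Analysis population.** Section 9.7 says that all enrolled patients will be analysed. It defines the reference population as enrolled, eligible patients with at least one follow-up visit completed. Neither 12 months of treatment nor study completion is required.
- **Expected time to progression.** Section 7.1.2: "The median locally assessed PFS was 7.8 months for Afinitor plus exemestane versus 3.2 months for exemestane plus placebo". For central assessment of the combination arm, section 7.1.2 gives 10.6 months and section 7.1.5.2 gives 11.0 months.

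Sections 9.1 and 9.3.4.8 keep each patient under observation until the last patient has been on study for 12 months, whether or not treatment has stopped.

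**The concern.** The number recruited and the number said to complete are both 200, so the precision statement implies that nobody is lost. It also attaches a 12-month treatment condition that the protocol's own efficacy background says most patients will not meet.

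Table 9-4 is the only quantitative support for the size of the study. A reader who takes its label literally will think that the primary incidences are estimated in 200 women who each had a year of exposure. The reported incidences will instead come from a cohort of about 200 less losses, in which more than half are likely to have stopped the combination before 12 months. The label also leaves the denominator open to argument. Restricting it to 12-month completers would remove women who stopped because of stomatitis or NIP, which are the events being counted.

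**Working it through.** **1. Reproduce the plan's figure.** The two-sided 95% Clopper-Pearson limits for x events in n patients are the 0.025 quantile of Beta(x, n − x + 1) and the 0.975 quantile of Beta(x + 1, n − x). With x = 80 and n = 200 they are 33.15% and 47.15%, that is 6.85 points below and 7.15 above. The protocol prints 33.2% and 47.2%, or 6.8 below and 7.2 above. All eight rows of Table 9-4 reproduce to within 0.1 point, so the arithmetic is correct for N = 200.

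**2. Check the 12-month treatment condition.** Every quoted median is below 12 months, so by definition fewer than half of such a population are alive and progression-free at 12 months. This step needs no distributional assumption. If treatment stops at progression or earlier, fewer than half are on treatment.

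To put a number on it, assume exponential times and treatment until progression, so that the share at 12 months is 0.5^(12 / median):

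| Median PFS (source) | Share at 12 months | Of 200 | Enrolment for 200 at 12 months (200 / share, rounded up) |
|---|---|---|---|
| 7.8 months (local, 7.1.2) | 0.344 | 69 | 581 |
| 10.6 months (central, 7.1.2) | 0.456 | 91 | 439 |
| 11.0 months (central, 7.1.5.2) | 0.469 | 94 | 427 |

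The local figure is the closest match to this study, where progression is investigator-assessed. Stopping for toxicity would lower all three shares. Section 9.7 caps enrolment at 15 per centre, so 25 centres give at most 25 × 15 = 375, which is below every figure in the last column. The cohort named in section 9.5 is therefore out of reach of the design on any of the quoted medians.

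**3. Check the completion condition alone.** Suppose *completed* only means evaluable under section 9.7. The protocol gives no loss rate, so 5% to 20% is assumed here. At 40% incidence:

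| Loss from 200 | n | Events | Exact 95% CI | Width (points) |
|---|---|---|---|---|
| 0% | 200 | 80 | 33.2–47.1% (protocol prints 47.2%) | 14.0 |
| 5% | 190 | 76 | 33.0–47.3% | 14.4 |
| 10% | 180 | 72 | 32.8–47.6% | 14.8 |
| 20% | 160 | 64 | 32.3–48.0% | 15.7 |

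The interval widens by 0.4 to 1.7 points over that range.

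**The case against.** The strongest reply is that nothing in the planned analysis depends on the faulty label. Section 9.7 fixes the population without a 12-month requirement, follow-up continues after treatment stops, and the table is right for N = 200. The 12 months may be a loose reference to the minimum observation period in section 9.1. The size is also justified by disease incidence and expected recruitment, and Annex 2 (item 9.1) says that there was no formal sample size calculation. Most of this stands, and it limits the consequence. It does not rescue the sentence, which speaks of treatment and not observation, and which still needs 200 completers from about 200 recruits.

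A reader might infer two stronger criticisms. Neither is supported.

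- **That the real precision is that of about 69 patients.** At 28/69 the exact interval is 28.9–53.1%, about 24 points wide. This applies only if incidence is estimated among 12-month completers, which the protocol does not plan. The figure of 69 also rests on the exponential assumption and the lowest of the three medians. For the same reason, the enrolment figures of 427 to 581 are no argument for a larger study.
- **That the protocol commits to one crude proportion over unequal follow-up.** Section 9.7.1 says only that "The analyses will be solely descriptive and comprise the description of the various items and the 95% CI", and section 9.7 leaves technical detail to the SAP, so a time-based estimate is not ruled out. Setting Table 7-1 against the cumulative risks in section 7.2.2 (grade 2 or worse pneumonitis: 6 + 3 = 9%, against 16% at 48 weeks) does not show the size of any distortion. Table 7-1 counts a single preferred term, 16% at all grades, whereas section 7.2.2 reports NIP or related events, 20% overall.

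**Conclusion.** Section 9.5 is wrong as written. Its precision statement is conditioned on 200 completed patients with 12 months of treatment. The protocol recruits about 200 with no loss allowance, analyses everyone eligible with one follow-up visit, and quotes PFS medians all below 12 months.

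That fewer than half would be on treatment at 12 months rests on two assumptions: that PFS here resembles the cited trial, and that treatment does not usually continue past progression. The range of 34% to 47% adds the exponential assumption.

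The effect on the planned analysis is modest. Under an assumed loss of 5% to 20%, the 40% interval is 14.4 to 15.7 points wide instead of 14.0. The defect lies in what the table claims to describe, and neither the table's calculation nor the number of patients is at fault.

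**What to change.** Amend section 9.5 and Table 9-4 as follows:

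1. State the precision for the section 9.7 reference population. Delete the word *completed* and the condition of 12 months' treatment.
2. State an assumed loss and show the exact intervals at the resulting evaluable number, for example 180 patients (32.8–47.6% at 40% incidence), with 190 and 160 as the range.

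Optionally, name a fixed time from first dose, such as 48 weeks, at which incidence is reported in all treated patients. This would give the incidence a defined horizon, and the estimator can be left to the SAP.

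The cost is a wording change and a recalculated table. No more patients are needed, and the stated precision becomes slightly less favourable.
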